## B.5 Study design

The MASTERS-D 2 study is a Prospective, Global clinical trial. Commercially available study devices will be used within their intended use.

The indication for the treatment of a patient will be at the discretion of the surgeon.

As such the assignment of a patient to a particular surgical intervention is not required within this clinical study protocol but falls within standard of care practice.

All fusion procedure patients will be screened consecutively against the eligibility criteria. Every effort will be made to enroll subjects in a consecutive manner.

Study enrollment is open to eligible subjects who in the opinion of the investigator are candidates for a minimally invasive lumbar fusion surgery.

The investigator or authorized designee must obtain written informed consent/ data release consent from the patient before any clinical study related activity takes place. The patient has the right to refuse and refusal will not affect the care of the patient. The patient can opt out at any time from the study. Refusal of study participation as well as enrollment into the study will be recorded on the screening log.

The following measures have been taken to avoid bias:

- Consecutive screening and enrollment is encouraged and enforced as much as possible.
  - When all inclusion/exclusion criteria are fulfilled for a patient, then the patient should be enrolled in this study. A screening log will be maintained at each site documenting the patients that have been screened and identified to be eligible or ineligible for the study, declined patients and enrolled patients.
  - In case the group with one of the approach procedures has reached the maximum amount of patients per procedure in a specific region, further enrollment of subjects into the procedure will be terminated. An email will be sent to the participating sites to inform the investigators when the enrollment for a specific procedure is complete.
- A multi-center design is used to help ensure a representative sample of surgeons performing the procedure and to ensure a reasonable enrollment period
- Only surgeons that have adequate experience (> 30 minimally invasive lumbar fusion procedures) can participate
- Site training will be performed to assure full understanding and engagement to comply with the study design and all protocol requirements
- Preferably, the ODI outcome measurements at 1, 3 months and 1, 2, 3, 4, 5 year follow up will be done by site staff different than the surgeon who operated the patient. The site staff will be trained to collect the ODI outcome measurements in an independent way without influencing the patients.

## B.6 Randomization and blinding

Randomization and blinding is not applicable in this study.

## B.7 Sample size

The primary objective is to evaluate if DDD patients operated for spondylolisthesis fare equally well regardless of the surgical procedure (anterolateral or posterior) performed, measured by the improvement of Oswestry Disability Index (ODI) 3 months after the surgery.

For the initial sample size calculation “equally well” was defined as a difference in ODI improvement at 3 months between groups within the range of (-7.5, 7.5) points. However, taking into account literature (74, 75) and the opinion of the Study Advisory board the equivalence range was increased to (-10, 10) points. As patient enrollment is slower than initially forecasted, the increase in equivalence range also allows completing enrollment timely.

If the difference in ODI improvement at 3 months between the anterolateral procedures group and the posterior procedures group is within the range of (-10, 10) points, the anterolateral and posterior treatment options will be considered equivalent in terms of effectiveness.

Assuming that the standard deviation for ODI improvement at 3 months is 20 for both groups (anterolateral and posterior) and there is no difference in the mean ODI improvement at 3 months, with 80% power and 5% alpha level, the sample size per group is 70 in order to claim equivalence of the primary endpoint between two groups with equivalent margin (-10, 10)

Estimated sample size per group (anterolateral procedures versus posterior procedures):	70
Estimated total sample size for spondylolisthesis patients with DDD:	140

From the MASTERS-D study it is known that approximately 50% of the patients with degenerative disc disease have spondylolisthesis  $\geq$  grade I. Hence the required total sample size is  $140/0.5 = 280$ .

The study is anticipated to enroll 350 patients. The amount of patients with spondylolisthesis versus non-spondylolisthesis will be monitored during the study. In case the study team identifies that the target amount of spondylolisthesis patients for the anterolateral procedures and posterior procedures might not be reached, the sites might receive instruction to limit the enrollment of non-spondylolisthesis patients. This action will secure the enrollment of target sample size as calculated for the primary endpoint. Additionally, it might be decided to stop patient enrollment completely when the required sample size for the primary endpoint has been reached.

It is expected that approximately 350 patients will be enrolled in this study from approximately 30 sites in Europe, Middle East, Latin America and Asia Pacific. This study will be open for enrollment to other countries in order to meet the required patient numbers. Sites have been selected based upon an anticipated enrollment for each minimally invasive fusion procedure. Consecutive enrollment will apply per minimally invasive procedure (i.e. ALIF, OLIF, DLIF, PLIF, TLIF and or MIDLF).

To allow the different regions to contribute patients to this study, a maximum enrollment per country/region might be defined during the course of the study. This will be timely communicated to the investigators and they will be requested to stop enrollment when the country/regional anticipated maximum number of patients has been reached. Patient enrollment limits per site for each country/region are indicated in Table 1. These limits may be subject to change during the course of the study and will be communicated as appropriate to the investigators and EC/IRB, if required.

The distribution of the procedures differs among the regions. Patient distribution across different surgical procedures will be in accordance with natural distribution in the country, but the study will aim to balance the

subjects between the procedures. Nevertheless, a minimum enrollment of 20 patients in each procedure (ALIF, OLIF, DLIF, PLIF, TLIF or MIDLF) is required for the study. A broad usage of both anterolateral and posterior lumbar fusion procedures is encouraged at all sites even though it is acknowledged that a user preference will apply. Enrollment limits per procedure have been defined for sites in China as these sites are allowed to enroll more patients than sites in other regions (Table 1). Investigators will be requested to stop enrollment when the maximum enrollment for that procedure at their site has been reached.

**Table 2: Overview of patient enrollment limits in Europe, Latin America, Middle East and Asia Pacific per site and per procedure.**

REGION	EUROPE	LATIN AMERICA	CHINA	KOREA
Enrollment max per site	40	20	120	20
Enrollment maximum per procedure for each site*	40	20	75	20
Estimated Number of sites	21	3	3	3

\* Enrollment limits per procedure might change to obtain a better distribution of procedures amongst the sites and regions and reach the minimum enrollment of 40 patients in each procedure. Any change in enrolment limitations will be communicated to the sites.

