## **G DATA ANALYSIS AND REPORTING**

### **G.1 Analysis of clinical data**

For the purpose of the analysis, all subjects who are enrolled and undergo a minimally invasive lumbar fusion procedure will be included in the analyses. All the analyses will be based on observed data. No missing data will be imputed.

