#### **G.1.1 Analysis of Primary Endpoint**

To evaluate whether the primary endpoint improvement in ODI at 3 months is equivalent for the spondylolisthesis DDD subjects treated with anterolateral approaches and the ones treated with posterior approaches, the two-sided 95% confidence interval for the mean difference of ODI improvement at 3 months will be calculated. If the 95% CI is within the equivalent range of (-10, 10), then the primary objective is met. In addition, the paired t-test will be carried out for each group to see whether the ODI improvement at 3 months from baseline is significant.

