4.2. Secondary Objectives and Endpoints

The secondary objectives include:

1. To evaluate whether DDD patients without spondylolisthesis fare equally well regardless of the surgical procedure (anterolateral or posterior) performed, as measured by endpoint which is defined as improvement of ODI at 3 months as compared to baseline.
2. To observe and document clinical and radiological outcomes through 5-year follow-up (except for ODI at 3 months). Endpoints include improvement of ODI as compared to baseline, improvement of VAS back- and leg pain intensity as compared to baseline, improvement of EQ-5D as compared to baseline, neurological success, fusion success, secondary surgeries at index and /or adjacent level(s) and adverse events (AE).
3. To observe and document the patients' short term recovery after surgery. Endpoints include time needed for first ambulation and surgery recovery day.
4. To document health resources consumption and perform economic analyses.
5. To observe and document the patient profile when choosing a particular minimally invasive fusion procedure.

5. Determination of Sample Size

Taking into account the literature information and the opinion of the Study Advisory Board, the "equally well" is defined as the mean difference in ODI improvement at 3 months between the anterolateral and posterior group is within the equivalence range of (-10, 10) points, which indicates if the mean difference between the anterolateral procedures group and the posterior procedures group is within the range of (-10, 10) points for the ODI improvement at 3 months, the anterolateral and posterior treatment options will be considered equivalent in terms of effectiveness.

Assuming that the standard deviation for ODI improvement at 3 months is 20 for both groups (anterolateral and posterior) and there is no difference in the mean ODI improvement at 3 months, with 80% power and 5% alpha level, the sample size per group is 70 and 140 in total in order to claim equivalence of the primary endpoint between two groups with equivalent margin (-10, 10).

From the MASTERS-D study it is known that approximately 50% of the patients with degenerative disc disease have spondylolisthesis \geq grade I. Hence the required total sample size is $140/0.5 = 280$.

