The study is anticipated to enroll 350 patients. The amount of patients with spondylolisthesis versus nonspondylolisthesis will be monitored during the study. In case the study team identifies that the target amount of 70 spondylolisthesis patients per group for the anterolateral procedures and posterior procedures might not be reached, the sites might receive instruction to limit the enrollment of non-spondylolisthesis patients. This action will secure the enrollment of target sample size as calculated for the primary endpoint.

6. Statistical Methods

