6.2. General Methodology

In this study, the two-sided 95% CI will be conducted to test hypothesis for primary and the first secondary objectives. For other analyses without hypothesis testing, the analyses are descriptive in nature. In general, the categorical variables will be summarized using frequency tables and continuous variables will be summarized using mean, standard deviation, median, minimum and maximum.

Time-to-event (life table method) will be performed to estimate the cumulative event rate up to 5 years for secondary surgery at index levels or adjacent levels and AEs.

Time-to-event analysis will be conducted for fusion success.

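### The 70 per group gives 80% power only with a 90% confidence interval; under the planned 95% interval rule power is about 67% before any ANCOVA gain, and 80% needs 86 evaluable per group

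*Protocol*

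**What the plan says.** Protocol B.7 assumes an SD of 20 for ODI improvement in each group, no true difference, and an equivalence range of (-10, 10). It concludes that, "with 80% power and 5% alpha level, the sample size per group is 70 in order to claim equivalence of the primary endpoint". SAP section 5 makes the same statement: "with 80% power and 5% alpha level, the sample size per group is 70 and 140 in total". Neither says whether the 5% is split between the two one-sided tests or applied to each.

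The decision rule in Protocol G.1.1 is a two-sided 95% confidence interval: "If the 95% CI is within the equivalent range of (-10, 10), then the primary objective is met". SAP 6.9.1 uses the same rule, applied to the least-squares mean difference from an ANCOVA with baseline ODI as covariate. SAP 6.2 confirms that "the two-sided 95% CI will be conducted to test hypothesis for primary and the first secondary objectives".

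The figure of 70 also steers enrolment. SAP section 5 allows sites to be told to limit non-spondylolisthesis patients if "the target amount of 70 spondylolisthesis patients per group for the anterolateral procedures and posterior procedures might not be reached". B.7 divides 140 by 0.5 to reach a required total of 280, anticipates 350, and adds that "it might be decided to stop patient enrollment completely when the required sample size for the primary endpoint has been reached". On missing data, G.1 says: "No missing data will be imputed".

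**The concern.** Requiring a two-sided 95% interval to fall inside the margin is the same as two one-sided tests at 2.5% each. If the sample size was worked out at 5% per test, the stated 80% belongs to a more lenient rule than the one planned, and the true power at the target is lower.

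This is the only primary objective. If enrolment stops at the documented target and ANCOVA gains nothing, two approaches that truly do equally well would fail to be declared equivalent about one time in three, rather than one in five. Stopping there is a realistic prospect: B.7 lists the permission to stop, and it explains the wider margin partly by timing ("As patient enrollment is slower than initially forecasted"). Because missing 3-month ODI is not imputed and the 70 carries no allowance for loss, 70 enrolled may mean fewer than 70 evaluable.

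**Working it through.** **Inputs (Protocol B.7, SAP section 5).** SD σ = 20 in both groups; margin m = 10; true difference 0; power 80%; equal groups.

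**Formulae.** Normal approximation: n per group = 2·[σ·(z₁₋ₐ + z₀.₉₀)/m]², where a is the level of each one-sided test; z₀.₉₀ appears because the 20% type II error is shared between the two limits. Exact power: the probability that the estimated difference plus and minus t₁₋ₐ,df·s·√(2/n) stays inside ±10, integrated over the chi-square distribution of s², with df = 2n − 2.

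**Reproducing the 70.** With a = 0.05: n = 2·[20·(1.645 + 1.282)/10]² = 68.5, so 69. The exact calculation gives 79.9% at 69 and 80.6% at 70. The plan's 70 is therefore the exact minimum for a 90% interval rule.

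**Applying the planned rule.** With a = 0.025: n = 2·[20·(1.960 + 1.282)/10]² = 84.1, so 85.

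| Evaluable per group | Power, 90% interval | Power, 95% interval |
|---|---|---|
| 69 | 79.9% | 66.1% |
| 70 | 80.6% | 67.2% |
| 85 | 89.1% | 79.98% |
| 86 | 89.5% | 80.6% |

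A simulation of 200,000 trials at 70 per group gave 67.3% for the 95% rule. The exact requirement for 80% is 86 per group, or 172 patients.

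The superseded figure in the change history points to the same convention: with margin 7.5, a = 0.05 gives 121.8, so 122 as listed there, whereas a = 0.025 gives 149.4.

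**Losses at the target (5% and 10% are assumptions).** 70 enrolled per group leaves 66 or 63 evaluable, and power of 62.7% or 59.0% under the 95% rule.

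**If all 350 are enrolled (equal split, 95% rule, no ANCOVA gain).** The 50% share is from B.7; 52.8% is the share reported for the predecessor study in Protocol A.1.1.

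| Spondylolisthesis share | No ODI missing | 5% missing | 10% missing |
|---|---|---|---|
| 50% | 87 per group, 81.3% | 83, 78.6% | 78, 74.7% |
| 52.8% | 92 per group, 84.2% | 87, 81.3% | 83, 78.6% |

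Unequal groups also cost power: 175 patients split 70 and 105 give 79.3%, and 65 and 110 give 77.7%.

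**Possible gain from ANCOVA.** Residual SD = 20·√(1 − ρ²), where ρ is the correlation of baseline ODI with improvement, and one degree of freedom is lost. At 70 per group under the 95% rule (ρ is assumed; the documents give none):

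| ρ | Residual SD | Power |
|---|---|---|
| 0.3 | 19.08 | 73.7% |
| 0.4 | 18.33 | 78.7% |
| 0.5 | 17.32 | 84.8% |

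Power reaches 80% at a residual SD of about 18.1, which is ρ of about 0.42.

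**Type I error.** With a true difference of 10 and 70 per group, equivalence is declared with probability 0.025 under the 95% rule and 0.050 under a 90% rule.

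**The case against.** The strongest reply is that the 70 is correct arithmetic under a common equivalence convention, 5% per one-sided test, so the fault is a mismatch between sizing and analysis. That describes the cause well, but the stated 80% is still not the power of the stated test.

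Second, 67% is not the power of the SAP's own analysis, which adjusts for baseline ODI. Improvement contains baseline, so a sizeable correlation is plausible. If baseline and 3-month SDs were equal (an assumption), ρ = √((1 − r)/2), where r is the baseline to 3-month correlation. Power at 70 per group would then be 91% at r = 0.3, 85% at r = 0.5, 80% at r = 0.64 and 74% at r = 0.8. This stands as a reason to call 67% the no-gain case. It does not rescue the 80%: both sample-size sections use the unadjusted SD, neither gives a correlation, and Protocol G.1.1 specifies no covariate adjustment.

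Third, stopping is only permitted, 350 is the anticipated enrolment throughout, and in a non-randomised study the larger group may well exceed 70 when the smaller reaches it: 70 and 80 give 71.8%, 70 and 90 give 75.3%. These points soften the shortfall. They do not secure the power, since the plan calls 280 the required total and an even split is not assured.

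Fourth, the wide 3-month window and collection of out-of-window visits should limit missing ODI. That is fair, and the loss rates above are assumptions.

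**Conclusion.** The concern holds. On the plan's own inputs, the stated 80% is wrong for the planned 95% interval rule. Power at 70 evaluable per group is 67.2% without an ANCOVA gain, and 80% needs 86 per group. The shortfall could disappear if the ANCOVA residual SD is about 18.1 or less, or nearly so if all 350 patients are enrolled in balanced groups with very little missing ODI. The documents state no such residual SD and do not guarantee that enrolment. The error affects power only: a positive result under the 95% rule remains valid. It needs correcting because the number it produces serves as the enrolment target and as a possible point to stop.

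**What to change.** Keep the 95% interval rule and make these changes:

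- **Protocol B.7 and SAP section 5, power:** state the level of each one-sided test. Restate power at 70 evaluable per group as about 67% without covariate gain, or state and justify an ANCOVA residual SD of about 18.1 or less.
- **Protocol B.7 and SAP section 5, target:** stop treating 70 per group as the size at which enrolment may end. Aim for about 86 with an evaluable 3-month ODI in each group.
- **Protocol B.4 and SAP 6.9.1:** write the hypotheses with the margin (H0: |difference| ≥ 10; HA: |difference| < 10). As written, HA is exact equality, which the interval rule does not test.

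**Cost.** The 172 evaluable patients need 172/0.5 = 344 enrolled at a 50% share, so 350 suffices only if fewer than 2% lack the 3-month ODI (3/175 = 1.7%). With 5% missing, 86/0.95 rounds up to 91 per group, or 182. That fits within 350 only if the share is at least 182/350 = 52%, which means using the existing option to hold non-spondylolisthesis enrolment to about 168. If this is not feasible, report the lower power.

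Switching to a 90% interval would also make the documents agree, but it would relax the primary criterion mid-study after the margin has already been widened. It would need justification before the primary data are examined, and edits to Protocol G.1.1 and SAP sections 3, 6.2, 6.5 and 6.9.1.

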## **E.10 Subject accountability**

Patients may withdraw from the study at any time and for any reason. Stop of data collection for patients in the study may occur in the following cases:

- Withdrawal of consent by patient
- Patient lost-to-follow-up
- Patient death
- Patient did not undergo the instrumented lumbar fusion as defined in this protocol

If a patient is withdrawn from the study, the reason for withdrawal shall be recorded in the eCRF and in the subject's hospital record. Subjects withdrawn from the study will only be replaced when patients did not undergo the instrumented lumbar interbody fusion with posterior fixation as defined in this protocol and if the enrollment is still open. In that case only, these patients will not contribute to the site and region specific enrollment limits nor to the maximum amount of patient enrollments per procedure.

Compliance to the minimum recommended follow-up schedule is essential to enable the analysis of the results in a scientifically sound and meaningful way. If, for whatever reason, the patient follow-up cannot be scheduled within the time window or occurred outside the time window, it is still essential to schedule a follow-up visit and to document the patient data at a date as close as possible to the calculated follow-up date.

Patients that are lost-to-follow-up should be avoided as much as possible and investigators are urged to do their utmost best to maintain patient's follow-up compliance as per CIP.

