6.4. Handling of Missing Data and Dropouts

All data analyses will be based on the observed data. Missing data due to lost to follow-ups will not be imputed. For study subjects included in the primary analysis dataset who drop out or withdraw from the study, data collected before the occurrence of dropout or withdrawal will be included in analysis.

This document is electronically controlled. Printed copies are considered uncontrolled.

Confidential

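### The option to stop enrolment early counts enrolled patients, but 70 per approach is the number that must be analysed, so using the option could leave the primary comparison below its stated power

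*Protocol*

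**What the plan says.** Protocol B.7 sets out the calculation: "Assuming that the standard deviation for ODI improvement at 3 months is 20 for both groups", "there is no difference in the mean ODI improvement at 3 months", an equivalence range of ±10 points, and "with 80% power and 5% alpha level, the sample size per group is 70". The resulting 140 is divided by 0.5, the expected share with spondylolisthesis, to give 280. Anticipated enrolment is 350.

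B.7 then describes monitoring. If the spondylolisthesis target looks at risk, sites may be told to limit other patients, and "This action will secure the enrollment of target sample size as calculated for the primary endpoint". The next sentence adds that "it might be decided to stop patient enrollment completely when the required sample size for the primary endpoint has been reached". SAP section 5 repeats the monitoring, with a target of 70 per group, but not the option to stop.

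Four other provisions bear on how many enrolled patients reach the analysis:

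- Protocol E.2 counts a patient as enrolled when the consent or data release form is signed.
- SAP 6.1.3 restricts the analysis set to patients who received the defined fusion.
- Protocol G.1 analyses observed data only, and SAP 6.4 says "Missing data due to lost to follow-ups will not be imputed".
- Protocol E.10 says "Subjects withdrawn from the study will only be replaced when patients did not undergo the instrumented lumbar interbody fusion with posterior fixation", and only while enrolment is still open.

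**The concern.** The calculation yields a number of patients with an analysable outcome. The monitoring and stopping text, read naturally, counts patients who have consented. Between consent and the 3-month ODI a patient can miss the defined fusion, withdraw, be lost or miss the assessment. B.7 has no term for this, because dividing by 0.5 corrects only for prevalence.

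Nothing later restores the number. Losses after surgery are not replaced, and closing enrolment also ends replacement of patients who never had the defined fusion. Protocol G.1.4 finalises the primary result once all subjects have reached 3 months, so a shortfall found then is permanent. The option could realistically be used, since B.7 itself says enrolment is slower than forecast. At stake is the chance of showing equivalence if it is true.

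**Working it through.** **Inputs.** SD 20, margin 10, true difference 0, power 80%, alpha 5%, 70 per group (protocol B.7, SAP 5). No loss rate is given, so 5%, 10% and 20% are assumptions.

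**Reproducing the plan's figure.** For two one-sided tests at 5% each with no true difference, the normal approximation is n = 2 × [SD × (z₀.₉₅ + z₀.₉₀) / margin]² = 2 × [20 × (1.645 + 1.282) / 10]² = 68.5, so 69 per group. Replacing z by t and integrating over the sample SD gives 80.6% power at 70 and 79.9% at 69, so 70 is the exact minimum. It contains no loss term.

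**Stopping with 70 enrolled in each group** (numbers analysed rounded down):

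| Assumed loss | Analysed per group | Power, 5% per side (plan's basis) | Power, two-sided 95% CI, unadjusted |
|---|---|---|---|
| 0% | 70 | 80.6% | 67.2% |
| 5% | 66 | 77.5% | 62.7% |
| 10% | 63 | 74.8% | 59.0% |
| 20% | 56 | 67.5% | 49.2% |

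**Unequal groups at the stop** (plan's basis; splits assumed). Both approaches must reach 70, so the larger group may exceed it. With 70 and 80 enrolled and 5% loss, 66 and 76 are analysed and power is 81.1%. With 70 and 90 enrolled and 10% loss, 63 and 81 are analysed and power is 81.2%.

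**If enrolment runs to 350.** 350 × 0.5 = 175 spondylolisthesis patients, or 87.5 per approach if evenly split; 87.5 × 0.8 = 70. About 20% could then be lost before the analysed number fell below 70. At an assumed 60:40 split the smaller group has 175 × 0.4 = 70 before any loss.

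**Decision rule.** The figure of 70 corresponds to 5% per side, which is a 90% interval. Protocol G.1.1 and SAP 6.9.1 require a two-sided 95% interval inside ±10, which is 2.5% per side. On that rule the exact calculation needs 86 analysed per group (80.6%; 85 gives just under 80%).

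**The case against.** The strongest defence is that B.7 does not say whether its trigger counts enrolled or evaluable patients. A sample size for the primary endpoint can be read as patients who have that endpoint, and the sentence about securing enrolment concerns a different action. If evaluable patients are meant, the attrition point falls away. This stands as an ambiguity, but the neighbouring wording and the definition of enrolment make enrolled the natural reading, and one sentence would settle it.

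Other mitigations also stand in part. The 3-month window is wide (−1.5/+3 months), a hospital visit is required, out-of-window data are still collected, and SAP 6.9 carries the last observation forward after further index-level surgery. These reduce missing ODI values but do not remove them.

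Three stronger readings are tempting and are not supported:

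- A reader might infer that the stated power is bound to be missed. The stop is optional, it is absent from the SAP, the default is 350, and uneven filling can keep power above 80% on the plan's basis.
- A reader might infer that the step from 280 to 350 is a 20% attrition allowance. No passage says so, and 87 per approach assumes an even split.
- A reader might infer that attrition is why 80% is not delivered. Under the planned 95% interval, unadjusted power is about 67% at 70 per group with complete data. The SAP's ANCOVA on baseline ODI may recover some power, but no baseline correlation is given.

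**Conclusion.** The point holds as a conditional weakness. If enrolment is stopped with both approaches at about 70 consented spondylolisthesis patients, the stated 80% is not protected: on the plan's own basis the loss is about 3 points of power at 5% missing, 6 at 10% and 13 at 20%. This rests on SD 20, no true difference, near-equal groups at the stop, a trigger that counts enrolled patients, and loss rates that are assumed. It does not apply if the trigger counts evaluable patients or if about 350 enrol with a roughly even split. It deserves correction because 70 has no slack, the text permits the stop, and the wording is easy to change.

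**What to change.** In protocol B.7 and SAP section 5, define both the monitoring target and the stop trigger as spondylolisthesis patients per approach who received the defined fusion and have both a baseline and a 3-month ODI. Otherwise continue to the planned 350. If enrolment stops earlier, or either group falls short, restate the power for the number analysed. Do not describe 350 as including a 20% allowance.

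Set the evaluable target to match the planned two-sided 95% interval: about 86 per group unadjusted, or a smaller number if a baseline correlation is stated and justified for the ANCOVA.

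The wording costs a few sentences. A stop decision may come later, by up to the time from consent to surgery plus the 3-month window, which runs to 6 months after surgery, in a study already enrolling slowly. Changing the trigger alone needs no increase over 350, although at an uneven split 350 may not yield the target in the smaller group. If 86 is adopted, 350 leaves almost no room for loss even with an even split (87.5 enrolled per approach), and the sponsor should say so.
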